5.8 Interim Analyses

An interim analysis of safety and technical utility of the embolic device (image visibility) and procedural assessments such as blinding, will be done after the 5 run-in patients complete the embolization procedure. Study reports on device/ procedure related complications are to be sent to the FDA following treatment of the five (5) run-in patients, and then after every 10 additional patients are randomized and treated (blinded).

No interim analysis for efficacy or futility are planned.

5.9 Multiplicity

The primary analysis of efficacy is tested at the two-sided alpha level of 0.20. In addition, secondary analyses will consider the alpha = 0.20 two-sided type I error. Secondary analyses will be examined in the order specified, and will not be corrected for multiplicity of testing. For safety outcomes, multiplicity will not be considered since this study is not powered on safety.

6.0 Missing Data

The clinical investigation team will make substantial efforts to ensure complete collection of data for all patients, and to accrue minimal loss to follow-up to optimize evaluation of the primary efficacy outcome. Our overall approach is to engage participants early on and keep them engaged through personal contact with the local center and access to information and resources that are relevant to them, their injury and their treatment. Furthermore, we do not expect the rates of missing data will be differential across treatment groups. As with most prospective studies, missing data will be unavoidable (even with excellent follow-up).

In order to impute the missing outcome data, analytic procedures will be utilized to ‘fill-in’ the missing body weights at 12 months’ post-procedure for those patients who do not have data on this primary endpoint. Specifically, a prediction model using completers (within each treatment group) will be created. In this case, a completer is a patient with data on body weight at 12 months’ post-procedure. The prediction model will include age, race, sex, and baseline body weight. We will then use multiple imputation to produce m random values for each missing 12 months’ post-procedure endpoint based on the prediction model. In this imputation process, the value of m will be set to 20, creating 20 “complete” data sets. Results of the two-sample t-test and rank test (and corresponding 95% confidence intervals) will be calculated over all 20 imputed

data sets based on the combination rules as specified by Rubin (1976, 1987)^{6,7}. Since only missing data at 12 months' post-procedure will be imputed, we assume that missingness is monotone.

Since the informative nature of missing data cannot be verified from the observed data, we will adopt a sensitivity analysis framework for reporting results. We will analyze data under a variety of modeling assumptions regarding how strongly the missingness mechanism is related to outcomes.⁵

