5.5 STRATEGIES FOR RECRUITMENT AND RETENTION

The targeted patient cohort is men and women aged between 21 and 70 years of various racial and ethnic backgrounds. Vulnerable patients (pregnant women, those who lack consent capacity, prisoners, children, employees, etc.) will be excluded as per the inclusion and exclusion criteria.

It is anticipated that approximately 1300 patients will be pre-screened to enroll 59 eligible subjects (based on prior experience in the BEAT Obesity trial) over a 24-month period. All subjects will be enrolled at the Johns Hopkins Hospital. Pre-screening will utilize an existing registry of patients from previous trials and patient referrals (weight management clinic referrals and self-referrals from advertising campaign). Identified or referred patients will be screened by phone using a telephone script.

Subjects will be followed for a period of 12 months. Retention strategies will include collecting multiple methods for contacting each participant and visit reminders. Subjects will receive payments of up to \$945 after the bariatric embolization (or control) procedure per the 12-month period, using the payment scheme tabulated below. Payment is given at 5 different intervals. Each test or log must be completed within the allotted range in order to receive payment. Payment may be prorated for weight management visits. For example, if a participant attended 4 weight management visits instead of 5 during weeks 4-8, they may receive \$40 during that time.

| Weeks 1-3 | Weeks 4-8 | Months 3-5 | Months 6-11 | Month 12 |
|------------------------------------|------------------------------------|------------------------------------|------------------------------------|----------------------------------|
| Food Log \$30 | Food Log \$20 | Food Log \$20 | Food Log \$30 | Food Log \$40 |
| Hunger Satiety \$30 | Hunger Satiety \$20 | Hunger Satiety \$20 | Hunger Satiety \$30 | Hunger Satiety \$50 |
| Hormone Test \$20 | Hormone Test \$30 | Hormone Test \$35 | Hormone Test \$40 | Hormone Test \$50 |
| | | MRI \$45 | MRI \$50 | MRI \$50 |
| | | Endoscopy \$70 | | |
| Weight Mgmt. (3 visits) \$40 | Weight Mgmt. (5 visits) \$50 | Weight Mgmt. (6 visits) \$55 | Weight Mgmt. (7 visits) \$60 | Weight Mgmt. (1 visit) \$5 |
| Blood Tests \$10 | Blood Tests \$10 | Blood Tests \$10 | Blood Tests \$10 | Blood Tests \$15 |
| Total \$130 | Total \$130 | Total \$255 | Total \$220 | Total \$210 |

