8.2.3 History & Physical

Medical history deemed clinically significant, relevant to the clinical trial objectives and design, will be collected per body system (allergy/immunology), auditory/ear, blood/bone marrow, cardiac arrhythmia, cardiac general, dermatology/skin), endocrine metabolic, gastrointestinal, hemorrhage/bleeding, hepatobiliary/pancreatic, infection, musculoskeletal/soft tissue, neurologic, ocular/vision, psychiatric, pulmonary/upper respiratory, renal/genitourinary, sexual reproductive function, vascular).

The use of concurrent medications (medications taken within 30 days of screening and during the conduct of the study) will be obtained and documented in source documentation and on the relevant eCRF.

All ongoing medical conditions and adverse events arising from treatment of those conditions present for 30 days or more are generally considered a part of the patient's baseline medical history and must be recorded where indicated.

A full physical examination, including actual measured height (required at screening only) and actual scale measured weight, will be performed by a qualified licensed individual. A review of body systems will include the following:

- Waist circumference
- General appearance, overall well-being and functional capacity
- Skin
- Head, Ears, Eyes, Nose, Throat (HEENT)
- Respiratory
- Cardiovascular
- Abdomen (including liver, gastrointestinal system)
- Musculoskeletal, extremities and mobility
- Neurological
- Vital signs: Assessments of vital signs (e.g., blood pressure, heart rate, temperature) will be performed at all study visits. When possible, blood pressure and heart rate will be determined after the patient has been in the sitting position for 5 minutes. Respiratory rate will only be obtained at baseline (i.e. at the weight management intake visit during screening).

A full physical examination as detailed above will be performed at baseline (weight management screening intake visit), 1-week, 2-weeks, and 1-month post-procedure. Vital signs, including weight, will be taken at all visits with weight management, however, waist circumference will only be measured at the weight management intake visit (screening period), on procedure day, and at the 1-month, 3-month, 6-month, and 12-month post-procedure weight management follow-up visits.

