3.6 Follow-up

Patient measures will be obtained post-procedure at weeks 1 and 2, and months 1, 3, 6, and 12.

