4.0 Analytical Populations

4.1 Full Analysis Set

The Full Analysis Set (FAS) to be used in the analyses of the efficacy outcomes will comprise all study patients who are randomized, undergo and complete the procedure to which they were assigned (embolization or sham surgery), and have at least one post-procedure outcome measure. The FAS will include any multiple imputed values for missing data from these patients.

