4.3 Completer Analysis Set

The Completer Analysis Set (CAS) will comprise all patients who were randomized, underwent and completed their assigned procedure, and who completed all post-procedure follow-up

visits (e.g. have at least the primary efficacy measures at post-procedure time points of weeks 1 and 2, and months 1, 3, 6, and 12). Analysis of the treatment effectiveness using CAS will be considered as sensitivity analysis to that performed using the FAS. However, if the efficacy outcome measures are missing completely at random (MCAR) or missing at random (MAR), then estimates of the treatment effect will be unbiased, and should produce results similar to those obtained using the FAS data with multiple imputation (MI) for the missing outcome measures.⁴

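### The imputation model for missing 12-month weight uses no post-procedure weight, so drop-out that depends on interim loss can bias the primary difference

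*SAP*

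**What the plan says.** SAP 6.0 imputes only the 12-month weight, separately by arm, from a model fitted to patients who have that weight: "The prediction model will include age, race, sex, and baseline body weight". Twenty imputed data sets are combined by Rubin's rules for the t-test and the rank test. The same section states "we do not expect the rates of missing data will be differential across treatment groups" and, because only month 12 is imputed, "we assume that missingness is monotone". It also promises sensitivity analyses for informative missingness, without naming a model or a range.

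SAP 4.1 puts the imputed values into the Full Analysis Set (FAS), which is used for efficacy. Entry requires that patients "have at least one post-procedure outcome measure".

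Interim weights are planned. SAP 3.6: "Patient measures will be obtained post-procedure at weeks 1 and 2, and months 1, 3, 6, and 12". Protocol 8.2.3: "Vital signs, including weight, will be taken at all visits with weight management". Protocol 8.2.14 schedules 8 weight-management visits in months 1-2, 6 in months 3-5, 2 in month 6 and 6 in months 7-12, which makes 22. The payment table in Protocol 5.5 agrees (3+5+6+7+1 = 22). Protocol 7.1 also asks for end-of-study assessments before withdrawal where possible.

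SAP 4.3 says of the Completer Analysis Set that if outcomes are missing completely at random (MCAR) or "missing at random (MAR), then estimates of the treatment effect will be unbiased", and that its results should resemble the FAS results.

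**The concern.** A patient who regained weight and then left is imputed as if he or she were a completer of the same arm, age, race, sex and baseline weight. If leaving depends on interim loss, the data may be missing at random (MAR) given the interim weights, but they are not MAR given the four listed predictors. The imputed values then carry the completers' selection into the primary t-test.

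Equal drop-out rates do not prevent this, because what matters is who leaves. The planned cross-check is weak as well. A completer comparison makes no use of interim weights, so SAP 4.3 invites the reader to take agreement between two similarly biased estimates as reassurance.

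**Working it through.** **Inputs from the documents** (SAP 3.8, 5.9, 6.0): mean losses 8 and 3.3 kg, so a difference of 4.7 kg; SD 7 kg; 27 per arm; 20% drop-out; two-sided alpha 0.20; 20 imputations.

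**Assumed, not in the documents:** correlation r of 0.5 to 0.9 between interim and 12-month loss; log odds of drop-out rising by 1 per SD of poorer interim loss.

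**1. The plan's own figure.** Noncentral-t power is 79.4% with 20 per arm and 80.9% with 21, so 21 is right. 21/(1 - 0.20) = 26.25, rounded up to 27. Standard error with 21 per arm: 7 × √(2/21) = 2.16 kg.

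**2. Selection in one arm, 20% drop-out in both.** Let z be standardized interim loss and p(z) = 1/(1 + exp(z - a)) the drop-out probability. An average of 20% needs a = -1.65. Those who stay then have mean z of d = E[z(1 - p(z))]/0.80 = 0.173. Their mean 12-month loss is too large by r × 7 × d:
- r = 0.5: 0.61 kg
- r = 0.7: 0.85 kg
- r = 0.9: 1.09 kg

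If only sham selects, completers show 4.09, 3.85 and 3.61 kg. If only BAE selects, they show 5.31, 5.55 and 5.79 kg. If both arms select identically around their own means, d cancels.

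Baseline predictors remove little of this. In a large-sample simulation, within-arm imputation from a baseline predictor correlated 0.1 with the change was within 0.02 kg of the completer bias. At correlation 0.3 about 90% of the bias remained. Adding the interim weight left 0.03 kg or less.

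**3. One common rule on observed loss.** With the true 4.7 kg difference, drop-out is about 25% in sham and 15% in BAE, giving d = 0.213 and 0.133. The shift is r × 7 × 0.080 = 0.28, 0.39 and 0.50 kg towards zero. With no true effect the two values of d are equal and nothing shifts.

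**4. Simulated trials** (3,000 per setting, 27 per arm, drop-out on the last recorded loss, spread over months 1-11). Here r is the correlation between adjacent scheduled visits, so late drop-outs' last weight is closer to month 12 and the shifts are larger than in steps 2 and 3. Mean estimate in kg at r = 0.5 / 0.7 / 0.9:

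| Drop-out | Planned model | With interim weights |
|---|---|---|
| Sham-only selection | 3.94 / 3.74 / 3.52 | 4.68 / 4.69 / 4.69 |
| BAE-only selection | 5.49 / 5.68 / 5.89 | 4.71 / 4.70 / 4.69 |
| Common rule | 4.30 / 4.22 / 4.15 | 4.69 at each r |
| Identical selection | 4.7 | 4.7 |

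Completers under sham-only selection: 3.87 / 3.69 / 3.47. If all drop-out follows month 1, sham-only selection gives 4.58 kg at r = 0.5 and 3.86 kg at r = 0.9 with the planned model, so early drop-out can make the shift as small as 0.12 kg.

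**5. The last weight must be in the model.** The right-hand column of the table assumes that drop-out acts through a weight in the sequence. If sham patients leave on their month-5 loss and month 3 is the last weight modelled, the estimate is still 4.39 / 4.41 / 4.54 kg. With the month-5 weight included it is 4.69 to 4.71 kg.

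**6. Error rate and power** (r = 0.7, one interim weight, 4,000 trials). With no true effect and poor responders leaving BAE only, a false finding in favor of BAE occurs in 17.8% of trials with baseline-only imputation, against a nominal 10%. It is 9.6% with the interim weight. The two-sided rejection rate moves only to 21.7%. With a true 4.7 kg and sham-only selection, power is 66%, against 80% under random drop-out and 82% with the interim weight.

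**The case against.** *Blinding makes arm-specific selection unlikely.* This stands in part. Participants and follow-up staff are blinded (Protocol 6.3), so a common rule on observed loss is the more natural case. It gives the smaller shift, towards zero, and none when there is no effect. Arm-specific drop-out is not excluded: several withdrawal triggers in Protocol 7.2, such as gastrointestinal bleeding, are listed risks of embolization in Protocol 2.3.1. The documents do not show that these track interim loss.

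*A sensitivity analysis is already promised* (SAP 6.0, Protocol 9.4.2). True, and it should stay. It has no stated parameters and does not change the primary estimate.

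*The completer set is not the one computed here.* This stands. The figures use patients with a 12-month weight, whereas SAP 4.3 also requires every earlier visit. A reader might infer that the Completer Analysis Set has exactly the same bias. The documents do not support that, only that it makes no correction for interim weight either.

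*The weights may not be in the database.* This stands as a point to confirm. Protocol 8.2.3 says weight is taken at weight-management visits, but nothing says those values are captured for analysis.

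*The fix can cost power.* This also stands. If all drop-out follows month 1 and r = 0.5, power is 77.5% with interim weights, or 74.5% if age, sex and race are kept, against 80.2% for completers. With drop-out spread over months 1-11 and random, it is 81-86%, against 80-82% for completers and 76-78% for the planned model.

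**Conclusion.** The omission is certain from the text. Its effect is conditional: it needs drop-out related to interim loss, together with either different selection by arm or a common rule and a true difference. Under the assumptions above, the shift is about 0.3 to 0.55 kg for a common rule and about 0.6 to 1.2 kg for one-arm selection, or less if drop-out is early. That is roughly an eighth to just over half of the 2.16 kg standard error (0.3/2.16 = 0.14; 1.2/2.16 = 0.56). It is worth fixing because the remedy is cheap, not because the trial is unsound.

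A reader might infer that the primary result will be biased, or that false positives will be inflated. The documents do not support either: they give no interim correlation and no drop-out mechanism, and several plausible mechanisms give no bias. A reader might also infer that only arm-specific selection matters, but step 3 shows otherwise when the arms differ. Nor does adding interim weights guarantee an unbiased result, since it still assumes MAR given the weights used.

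**What to change.** **SAP 6.0.** Keep the two-sample t-test and the within-arm multiple imputation. Add the observed post-procedure weights to the prediction model by sequential imputation:
- Use intervals that cover follow-up without gaps, for example weeks 1-2, months 1, 2, 3, 4-5, 6, 7-9, 10-11, then 12.
- In each interval take the last weight recorded at a study, weight-management or withdrawal visit. The last weight before drop-out then enters the model even when a patient simply stops attending.
- Use fewer intervals if about 21 completers per arm cannot support them.
- Keep baseline weight. Whether to keep age, race and sex is a trade-off for the sponsor's statistician.
- Replace the monotone-missingness sentence with a rule for filling intermittent gaps first.
- Confirm that weight-management weights are captured in the trial database.

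**SAP 4.3.** Replace the MAR statement with: *The completer comparison is unbiased under MCAR. Under MAR it can be biased when missingness depends on baseline or interim variables related to 12-month weight, including under a rule common to both arms if the arms differ. Agreement with the FAS result is therefore not evidence against bias.*

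Keep the SAP 6.0 sensitivity analysis as a separate check.

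**Cost.** SAP wording, slightly more programming, and the possible small power loss noted above when drop-out is early and the interim correlation low. The primary test, sample size and visit schedule do not change. Protocol 9.4.2 specifies no imputation model. If the sponsor regards this as a change to the primary analysis, SAP 1.0 calls for a protocol amendment as well.

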7.0 Standard Calculations

7.1 Age

Patient age will be calculated in years by the following formula:

Age (years) = Integer of [(date of procedure – date of birth)]/365.25

If only the month and year of either the patient's birth or date of procedure is known, then the day will be given by the 15th of the month.

7.2 Change from Baseline

The change for any continuous outcome at any follow-up time (t) from baseline is defined as:

Change from baseline (designated as Δ_t) = Outcome measurement at time t – Outcome measure at baseline.

7.3 Percent Change from Baseline

The Percent change for any continuous outcome at any follow-up time point (t) from baseline is defined as:

Percent change from baseline = (Outcome measurement at time t – Outcome measure at baseline) / (Outcome measure at baseline)

